**Table 8.5-1: Summary of Assumptions Used for Sample Size Calculations**

NI comparison	H1N1	H3N2	B strains
Test significance level, alpha (1-sided)	2.50%	2.50%	2.50%
Noninferiority Margin for the SCR comparison (%)	10	10	10
Assumed true SCR	73%	73%	40%
Power for SCR comparison tests for	99.45%	99.45%	91.29%

each strain (%)			
Global Power for 4 SCR Endpoints	82.42%		
Noninferiority Margin for the GMT ratio	1.5	1.5	1.5
Common Standard Deviation of $\log_e(\text{titer})$	1.2	1.2	1.2
Power for GMT ratio tests for each strain (%)	99.99%	99.99%	99.98%
Global Power for 4 GMT ratio Endpoints	99.96%		
Global Power for 8 Co-primary Endpoints	82.39%		
CBER Criteria	H1N1	H3N2	B strains
Test significance level, alpha (1-sided)	2.50%	2.50%	2.50%
Seroconversion Threshold	30%	30%	30%
Assumed true SCR	73%	73%	40%
Power for SCR	100%	100%	100%
Global Power for 4 SCR Endpoints	100%		
Threshold for Rate $\geq 1:40$	60%	60%	60%
Assumed True Rate $\geq 1:40$	91%	99%	64.6%
Power for Rate $\geq 1:40$	100%	100%	76.47%
Global Power for 4 <math>\geq 1:40</math> Endpoints	76.47%		
Global Power for the Second 8 Co-	76.47%		

primary Endpoints (CBER Criteria)
------------------------------------------

A safety database of  $N = 800$  has a 95% chance of detecting AEs that occur at a rate of 1 in 267. With a single stratum of 800 participants, the probability of observing at least one event for events with population rates of 1 in 300, 1 in 200, and 1 in 100 are 93.1%, 98.2% and 100%, respectively.

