The GLM specification is: Adjusted Analysis GMT Model: Log-transformed Post-vaccination HI Titer = Vaccine + Age Strata + Gender + Vaccination History [y/n] + Log-transformed Prevaccination HI Titer + Site + Age Strata*Vaccine.		
The measure of the unadjusted GMT ratio based on postvaccination GMTs only will		

Name of Sponsor: Seqirus Inc.	Protocol number: V118_20	Generic name of study vaccine(s): MF59-adjuvanted Quadrivalent Subunit Inactivated Egg-derived Influenza Vaccine (aQIV); Licensed MF59-adjuvanted Trivalent Subunit Inactivated Egg-derived Influenza Vaccine (aTIV-1); MF59-adjuvanted Trivalent Subunit Inactivated Egg-derived Influenza Vaccine Containing the Alternate B Strain (aTIV-2).
also be presented.		
In line with the FDA Guidance on seasonal inactivated influenza vaccines ( Guidance for Industry Clinical Data Needed to Support Licensure of Seasonal Inactivated Influenza Vaccines 2007 ). aQIV will be considered to be non-inferior to aTIV if, for each of the four strains, the following statistical criteria are met:		

• The upper bound of the two-sided 95% Confidence Interval (CI) for the ratio of the GMTs does not exceed 1.5. The GMT ratio will be calculated by <math>GMT_{aTIV}/GMT_{aQIV}</math>.

• The upper bound of the two-sided 95% CI for the difference between the SCRs does not exceed 10%. The difference in SCR will be calculated by <math>SCR_{aTIV} - SCR_{aQIV}</math>.

		
CBER Criteria:		
To achieve the co-primary CBER criteria:		

• The lower bound of the two-sided 95% confidence interval for the percentage of subjects achieving seroconversion for HI antibody should meet or exceed 30%.

• The lower bound of the two-sided 95% confidence interval for the percentage of subjects achieving an HI antibody titer <math>\geq 40</math> should meet or exceed 60%.

		
To meet the CBER criteria, both endpoints should be met for each strain included in aQIV arm.		
The statistical evaluation consists of the observed proportion together with the corresponding two-sided exact 95% confidence interval per strain. No adjustment for type I error for multiplicity is made.		

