## 8. STATISTICAL CONSIDERATIONS

### 8.1 Endpoints

#### 8.1.1 Primary Endpoints

##### 8.1.1.1 Co-Primary Immunogenicity Endpoints

The immunogenicity of study vaccines will be assessed 21 (i.e., on Day 22) days after vaccine administration by measuring the hemagglutination inhibition (HI) antibody titers to the four virus strains included in the vaccines.

The noninferiority of aQIV compared to aTIV-1, and to aTIV-2 will be assessed for the eight co-primary endpoints of HI geometric mean titer (GMT) and seroconversion rate (SCR) for each virus strain included in the vaccines as follows:

- The GMT ratio\* for the A/H1N1 strain
- The GMT ratio for the A/H3N2 strain
- The GMT ratio for the B strain (Yamagata lineage)
- The GMT ratio for the B strain (Victoria lineage)
- The difference between the SCR\*\* for the A/H1N1 strain
- The difference between the SCR for the A/H3N2 strain
- The difference between the SCR for the B strain (Yamagata lineage)
- The difference between the SCR for the B strain (Victoria lineage)

Immunogenicity results obtained from aTIV-1 and aTIV-2 for both A/H1N1 and A/H3N2 strains will be pooled for comparison with aQIV.

*\*The GMT ratio is defined as the geometric mean of the post-vaccination (Day 22) HI titer for aTIV-1 (or aTIV-2) over the geometric mean of postvaccination (Day 22) HI titer for aQIV.*

*\*\*The SCR is defined as the percentage of subjects with either a prevaccination HI titer < 1:10 and a post-vaccination HI titer  $\geq$  1: 40 or a prevaccination HI titer  $\geq$  1:10 and a  $\geq$  4-fold increase in postvaccination HI titer.*

The second co-primary immunogenicity objective for aQIV will be assessed 21 days after vaccine administration by applying CBER criteria for the elderly population for each of the 4 strains included in aQIV:

- The percent of subjects achieving seroconversion for HI antibody

- The percent of subjects achieving an HI antibody titer  $\geq 1:40$

The study is considered successful if the (16) co-primary endpoints are achieved.

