## 8.5 Sample Size and Power Considerations

aQIV will be tested against aTIV comparators. The treatment randomization ratio is 2:1:1 (aQIV: aTIV-1: aTIV-2). This study is powered to achieve 80% power to demonstrate noninferiority over 8 co-primary endpoints, seroconversion rates for 4 strains, GMT for 4 strains using a one-sided alpha of 0.025 for each comparison. No adjustment for multiple endpoints will be made.

For comparisons of SCR a noninferiority margin of 10% (aTIV – aQIV) will be employed. It is assumed that the SCRs for A/ H1N1, A/ H3N2 and B strains for TIV are 73%, 73% and 40% respectively. These estimates are based on the estimated SCR rates of historical data, namely study protocol V70\_27. It has been assumed that there is no difference in terms of SCR between aQIV and aTIV for all strains. For comparison of the GMT ratio, a noninferiority of 1.5 (aTIV/aQIV) will be employed. It is assumed that there is no difference between aQIV and aTIV (i.e., a ratio of 1) and that the standard deviation of log (titer) is 1.2.

Under these assumptions, N evaluable = 800 in the aQIV group and 400 in each aTIV group providing 800 and 800 subjects receiving aQIV and aTIV respectively for comparisons of A strains, and 800 and 400 subjects receiving aQIV and aTIV respectively for comparisons of B strains. This provides a total N evaluable = 1600. These numbers provide 99.45% power to detect differences in SCR for each A strain and 91.29% power for each B strain, providing overall 82.42% power for the 4 SCR tests.

For GMT ratio tests each A strain test will have 100% power and each B strain test will have 99.98% power, providing 99.96% power for the 4 GMT ratio tests and consequently 82.39% power for the 8 co-primary endpoints. Overall 1600 evaluable subjects will be required. Allowing for a 10% drop-out N=1778 subjects will be recruited (Sample size calculations were performed using PASS v12).

The immunogenicity was powered to meet the criteria prespecified in the CBER guidance for acceptable immunogenicity: namely,

- the lower bound of the two-sided 95% confidence interval for the percent of subjects achieving seroconversion should exceed 30%, and
- the lower bound of the two-sided 95% confidence interval for the percent of subject achieving HI antibody titer  $\geq 40$  should exceed 60%

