With a sample size of N=800 (evaluable) subjects for the aQIV group if the population SCR for A/ H1N1, A/ H3N2 and B strains for TIV is 73%, 73% and 40% respectively then the probability of observing a seroconversion rate that is significantly greater than 30% is approximately 100% (for the A/H1N1), 100% for A/H3N2 and 100% (for the B-strains).

With a sample size of N=800 (evaluable) subjects for the aQIV group if the population SP rates for A/ H1N1, A/ H3N2 and B strains for TIV is 91%, 99% and 64.6% respectively (as observed in V70\_27) then the probability of observing a SP rate that is significantly greater than 60% is approximately 100% (for the A/H1N1), 100% for A/H3N2 and 76.47% (for the B-strains).

**Table 8.5-1** summarizes the list of all co-primary endpoints with strains, the planned noninferiority margin and underlying assumptions used for the sample size computations.

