With a sample size of N=800 (FAS) subjects for the aQIV group if the population SCR for A/ H1N1, A/ H3N2 and B strains for TIV is 73%, 73% and 40% respectively then the probability of observing a SCR that is significantly greater than 30% is approximately 100% (for the A/H1N1), 100% for A/H3N2 and 100% (for the B-strains).

With a sample size of N=800 (FAS) subjects for the aQIV group if the percent of subject achieving HI antibody titer $\geq 1:40$ for A/ H1N1, A/ H3N2 and B strains for TIV is 91%, 99% and 64.6% respectively (as observed in V70_27) then the probability of observing a SP rate that is significantly greater than 60% is approximately 100% (for the A/H1N1), 100% for A/H3N2 and 76.47% (for the B-strains).

Table 5-1 summarizes the list of all co-primary endpoints with strains, the planned noninferiority margin and underlying assumptions used for the sample size computations.

Table 5-1: Summary of Assumptions Used for Sample Size Calculations

NI comparison	H1N1	H3N2	B strains
Test significance level, alpha (1-sided)	2.50%	2.50%	2.50%
Noninferiority Margin for the SCR comparison (%)	10	10	10
Assumed true SCR	73%	73%	40%
Power for SCR comparison tests for each strain (%)	99.45%	99.45%	91.29%
Power for SCR comparison tests for each strain (%)	99.45%	99.45%	91.29%
Global Power for 4 SCR Endpoints	82.42%		
Noninferiority Margin for the GMT ratio	1.5	1.5	1.5
Common Standard Deviation of $\log_e(\text{titer})$	1.2	1.2	1.2
Power for GMT ratio tests for each strain (%)	99.99%	99.99%	99.98%
Global Power for 4 GMT ratio Endpoints	99.96%		
Global Power for 8 Co-primary Endpoints	82.39%		
CBER Criteria	H1N1	H3N2	B strains
Test significance level, alpha (1-sided)	2.50%	2.50%	2.50%
Seroconversion Threshold	30%	30%	30%
Assumed true SCR	73%	73%	40%
Power for SCR	100%	100%	100%
Global Power for 4 SCR Endpoints	100%		

Threshold for HI titres $\geq 1:40$	60%	60%	60%
Assumed True percent of subject achieving HI antibody titer ≥ 40	91%	99%	64.6%
Power for percent of subject achieving HI antibody titer $\geq 40 \geq 1:40$	100%	100%	76.47%
Global Power for all 4 percents of subject achieving HI antibody titer ≥ 40e	76.47%		
Global Power for achieving the (CBER Criteria)	76.47%		

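### Global power for the CBER criteria is printed as 76.47%, the power for one B strain; both B strains must pass, and the tables' own product convention gives 58.5%

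*Protocol*

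**What the plan says.** Protocol Section 8.5 and SAP Section 5 give power strain by strain for the second co-primary objective. For the titer ≥1:40 criterion with 800 aQIV subjects, the Protocol text ends with "100% for A/H3N2 and 76.47% (for the B-strains"). The assumed true B-strain rate is 64.6% and the threshold is 60%.

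The summary tables then give two global figures for this objective, both 76.47%:

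- Protocol Table 8.5-1: one row for the four titer endpoints, and one beginning "Global Power for the Second 8 Co" for all eight CBER endpoints.
- SAP Table 5-1: "Global Power for all 4 percents of subject achieving HI antibody titer" and "Global Power for achieving the (CBER Criteria").

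The rule for passing is in the Protocol Synopsis, under the CBER criteria: "To meet the CBER criteria, both endpoints should be met for each strain included in aQIV arm". Protocol Section 8.1.1.1 adds: "The study is considered successful if the (16) co-primary endpoints are achieved". SAP Section 2.1.2 likewise requires all co-primary endpoints.

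For the non-inferiority objective, the same sections report global power that counts both B strains: "providing overall 82.42% power for the 4 SCR tests", and for titers "each B strain test will have 99.98% power, providing 99.96% power for the 4 GMT ratio tests".

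**The concern.** The tables have a single B-strain column, but aQIV contains a Victoria and a Yamagata strain and each must meet the criterion. A global figure equal to the one-strain figure means that only one of the two B-strain tests has been counted.

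Meeting the CBER criteria is a condition for study success, and Section 8.5 says the immunogenicity was powered to meet them. The titer criterion on the B strains is the weakest test in the design, so it largely sets the chance of success. A reader who takes 82.39% for non-inferiority and 76.47% for the CBER criteria from these tables will overestimate that chance.

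**Working it through.** **Inputs** (Protocol 8.5 and Table 8.5-1; SAP Section 5 and Table 5-1): 800 aQIV subjects; one-sided alpha 0.025; titer ≥1:40 rate for B strains 64.6% against 60%; seroconversion rate for B strains 40% against 30%; exact 95% confidence interval (Protocol 8.4.2.2.1). Printed non-inferiority powers: seroconversion 99.45% per A strain and 91.29% per B strain; GMT ratio 100% per A strain (text) and 99.98% per B strain.

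**Step 1: what 76.47% is.** Power for one B strain on titer ≥1:40:

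- Exact interval: the lower bound reaches 60% from 508/800 upward. P(X ≥ 508 | n = 800, p = 0.646) = 75.47%.
- Normal approximation with null standard error: SE₀ = √(0.6 × 0.4/800) = 0.01732 and SE₁ = √(0.646 × 0.354/800) = 0.01691. Φ[(0.046 − 1.96 × 0.01732)/0.01691] = 76.20%.
- Wald standard error: 77.66%. Null standard error with continuity correction: 75.04%.

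The printed 76.47% lies inside this range. It is the power for one strain and cannot already be a joint figure for two.

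**Step 2: how the same tables form global power.** Products over the four strains, with each B strain counted:

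| Row | Product over four strains | Printed | With one B strain only |
|---|---|---|---|
| Seroconversion, non-inferiority | 0.9945² × 0.9129² = 82.42% | 82.42% | 0.9945² × 0.9129 = 90.29% |
| GMT ratio | 1² × 0.9998² = 99.96% | 99.96% | 99.98% |
| All 8 non-inferiority endpoints | 0.8242 × 0.9996 = 82.39% | 82.39% | – |

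**Step 3: the same convention for the CBER rows.**

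- Four titer endpoints: 1 × 1 × 0.7647² = 0.5848, or 58.5%.
- Eight CBER endpoints: B-strain seroconversion power (40% against 30%, exact, at least 267/800) is 99.995% and the A-strain tests are at about 100%, so the product remains 58.5%.
- Gap to the printed figure: 76.47 − 58.48 = 18.0 percentage points.
- With the exact-interval power per strain: 0.7547² = 57.0%.

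**Step 4: sensitivity to dependence between the two B strains.** The documents give no correlation. Bivariate normal with each margin at 76.47%, correlations assumed:

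| Assumed correlation | Joint power |
|---|---|
| 0 | 58.5% |
| 0.3 | 61.6% |
| 0.5 | 64.0% |
| 0.7 | 66.9% |
| 0.9 | 71.0% |
| Results always coincide | 76.47% |

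The lowest value possible under any dependence is 2 × 0.7647 − 1 = 52.9%.

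**Step 5: all 16 endpoints (secondary).** By the same product rule, 0.8239 × 0.5848 = 48.2%. It cannot exceed 76.47%.

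**The case against.** The strongest reply is that neither document states a product or independence rule. Both B-strain results come from the same 800 subjects, so positive correlation is plausible, and 76.47% is a legitimate upper bound. All of that is true, and it means 58.5% is the independence value and not a certain one. It does not rescue the printed figure, which is labelled as power and not as a bound. It needs perfect dependence between the B strains, while the rows above it in the same table match independence.

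The product rule also does not fit every table cell. The GMT cells for the A strains read 99.99%, and 0.9999² × 0.9998² = 99.94%, not 99.96%. The printed 99.96% follows from the 100% in the text, so this looks like rounding. The seroconversion row has no such ambiguity and is enough to show that both B strains are counted.

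Two points limit the weight of the finding. The 80% target is set only for the eight non-inferiority endpoints, so no stated CBER target is missed, and the one-strain 76.47% is openly reported. The 48.2% for 16 endpoints is softer than the rest: it multiplies tests that reuse the same aQIV titers, positive dependence would raise it, and neither document prints such a row to be corrected.

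**Conclusion.** The concern holds. The two global CBER rows in Protocol Table 8.5-1 and SAP Table 5-1 carry a one-strain power where two B strains must pass, and they are inconsistent with the non-inferiority rows beside them. By the convention that reproduces those rows, global CBER power is 58.5%, an overstatement of 18.0 percentage points. This takes the printed per-strain 76.47% as given and assumes independence between strains. Moderate positive correlation narrows the gap without closing it. Using the planned exact interval instead of the printed per-strain figure gives 57.0%, so the conclusion does not depend on the per-strain method. The error is one of disclosure: the per-strain figures, the decision rule and type I error stand.

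**What to change.** In both tables, change the two global CBER rows from 76.47% to about 58.5%. Add a note that this uses the same independence convention as the non-inferiority rows, and that 76.47% is the ceiling if the two B-strain results always coincide. Optionally, add one row for the 16-endpoint success rule: about 48% by the same product rule, at most 76.47%, with a remark that shared subjects would raise the product figure.

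The cost is two rows and a note in each of two tables. Sample size, endpoints, thresholds and analyses do not change. The only drawback is a less favourable stated power.

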## **8.6 Interim Analysis**

No interim analysis is planned for this study.

## 9. SOURCE DOCUMENTATION, STUDY MONITORING AND AUDITING

In order to ensure consistency across sites, study monitoring and auditing will be standardized and performed in accordance with the Sponsor's or delegated contract research organization's (CRO) standard operating procedures and applicable regulatory requirements (eg, FDA, EMA, and ICH guidelines).

Prior to enrollment of the first study subject, Seqirus or delegate will train investigators and/or their study staff on the study protocol, all applicable study procedures, documentation practices and all electronic systems. CRFs supplied by the Sponsor must be completed for each enrolled subject (see [Section 8.3.1, All Enrolled Set](#) for definition of enrolled subject). Documentation of screened but not enrolled subjects must be maintained at the site and made available for review by the site monitor. Data and documents will be checked by the Sponsor and/or monitor.

### 9.1 Source Documentation

Prior to the start of the study, the site staff participating in the study conduct will be instructed on what documents will be required for review as source documents. The kinds of documents that will serve as source documents will be agreed between Sponsor or delegate and Investigator and designees and specified in the SDA prior to subject enrollment.

In addition, source documentation **must** include all of the following: subject identification (on each page), eligibility and participation, proper informed consent procedures, dates of visits, adherence to protocol procedures, adequate reporting and follow-up of adverse events, documentation of prior/concomitant medication/vaccines, study vaccine receipt/dispensing/return records, study vaccine administration information, any data collected by a telephone conversation with the subject and date of completion and reason.

The subject must also allow access to the subject's medical records. Each subject must be informed of this prior to the start of the study and consent for access to medical records that may be required in accordance with local regulations.

All safety data reported by subjects must be written down in source documents prior to entry of the data into CRFs. If there are multiple sources of information (e.g., Diary Card, verbal report of the subject, telephone contact details, medical chart) supporting the diagnosis of an adverse event, these sources must be identified in the source documents, discrepancies between sources clarified, the ultimate diagnosis must be justified and written in the source documents, and this diagnosis must be captured in the Adverse Event CRF (AE CRF). The AE CRF must also capture which source(s) of information were used to determine the adverse event (e.g. subject recall, medical chart, Diary Card).

## 9.2 Study Monitoring, Auditing and Source Data Verification

Prior to enrollment of the first study subject, Seqirus or its designee (eg, a CRO) will develop a Clinical Monitoring Plan to specify how centralized and/or on-site monitoring, including clinical specimens reconciliation, will be performed for the study. Study progress will be monitored by Seqirus or its designee as frequently as necessary to ensure:

- that the rights and well-being of human subjects are protected
- the reported study data are accurate, complete, and verifiable from the source documents and
- the conduct of the study is in compliance with the current approved protocol/amendment(s), GCP and applicable regulatory requirements

Contact details for the Seqirus team or its designee involved in study monitoring will be provided to the Investigator. Study data recorded on CRFs will be verified by checking the CRF entries against source documents in order to ensure data completeness and accuracy as required by the study protocol.

Data verification may also be performed through a centralized review of data (eg, checking for outliers or other anomalies). Additional documents such as the Investigator Site File, pharmacy records, and informed consent documentation must also be available for review if requested. Arrangements for monitoring visits will be made in advance in accordance with the monitoring plan, except in case of emergency.

The Investigator and/or site staff must make source documents of subjects enrolled in this study available for inspection by Seqirus or its representative at the time of each monitoring visit and Sponsor audits, when applicable. These documents must also be available for inspection, verification and copying, as required by regulations, by officials of the regulatory health authorities (e.g. FDA, EMA and others) and/or ECs/IRBs. The Investigator and study site staff must comply with applicable privacy, data protection and medical confidentiality laws for use and disclosure of information related to the study and enrolled subjects.

## **10. DATA MANAGEMENT**

### **10.1 Data Entry and Management**

In this study, all clinical data (including, but not limited to, AE/SAEs, concomitant medications, medical history, and physical assessments), safety data, and immunogenicity data will be entered onto case report forms (CRFs) in a timely fashion by the Investigator and/or the Investigator's dedicated site staff. Data entered onto CRFs are stored on a secure website. The data collected on this secure website are assimilated into an electronic data capture (EDC) system, which is compliant with Title 21 Part 11 policies of the Code of Federal Regulations ([FDA, 1997](#)). The data system includes password protection and internal quality checks. The EDC system will be designed and validated by the Sponsor prior to activation for data entry by sites. The Investigator or designated delegate must review data entered and electronically sign the CRFs to verify their accuracy.

Access to the EDC system for data entry or review will require training and distinct individual access code assignments to those site staff members who will be entering study data and those involved in study oversight who may review study data. Data are collected within the EDC system, to which the Sponsor and site monitors have exclusively "read only" access.

